1. PROTOCOL INFORMATION

Title: Effects of electrotherapy on cervical spine proprioception, pain, anxiety, and disability in adults with subclinical neck or upper quadrant pain.

Funding Source: School of Allied Health Professions (SAHP)

Phase of Study: N/A

Version Date of Protocol: N/A

4. STUDY INFORMATION

Location(s) of Research Activity: SAHP Neuroscience Research Laboratory- [name].

Expected Start/Stop Dates of Research: July 1, 2022-June 30, 2023.

Special Time Sensitivities: N/A

Type of Research: Experimental

5. INCLUSION / EXCLUSION CRITERIA

Inclusion criteria: Subjects will be adults between 20-40 years of age currently enrolled as students at Loma Linda University. There will be three groups. The

normal group will include twenty subjects with no neck and/or quadrant pain. The control group will include twenty subjects with neck and/or upper quadrant chronic subclinical pain and the intervention group will include twenty subjects with neck and/or upper quadrant chronic subclinical pain.

Exclusion criteria: Individuals currently receiving clinical pain treatment, pain medications within six hours of data collection, acute pain (control and intervention groups), individuals with electrotherapy contraindications, and unwilling to receive daily SMS text message home program reminder. Exclusion criteria will be determined by self-report using a questionnaire.

6. SUBJECT RECRUITMENT & SCREENING

This study will have a sample size of 60 adults (males and females) between 20 to 40 years of age. This sample size will provide us with enough power to detect the needed effect size. The estimated attrition rate is 15 percent. The participants will be recruited from the student population at Loma Linda University via flyers, posters, hand-outs, mass emails, and word of mouth. The phone script will be used when potential subjects contact us after seeing the flyer.

7. INFORMED CONSENT PROCESS

The informed consent will be conducted by [name] in the SAHP Neuroscience Research Laboratory with a single potential subject at a time. Participants will have the opportunity to ask questions before deciding to participate. Those participants who meet inclusion criteria will be identified by a code on all documents other than their signature on the informed consent. Twenty participants with no pain will be in the normal group. Forty participants with chronic subclinical neck or upper quadrant pain will be randomized (random number table will be used) into two groups: twenty subjects in the control group, and twenty subjects in the intervention group. All participants' records will be stored in a locked cabinet, in a locked office and stored on a secure drive.

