- 1) To measure the immediate and short-term effects of TENS on subclinical neck or upper quadrant pain with the VAS, anxiety with the State-Trait Anxiety Inventory for Adults™, disability with neck disability index (NDI), disability and cervical spine proprioception Noraxon 3D Inertial Motion Capture System in subjects 20-40 years of age.
- 2) To measure pain, anxiety, disability, and cervical spine proprioception in subjects with and without neck or upper quadrant pain.
- 3) To compare compliance of TENS home usage in groups with and without short message system (SMS), text message, reminders.

c. Procedures involved (Research Interventions)

There will be three groups as follows: twenty subjects with no pain in the normal group; forty subjects with chronic subclinical neck or upper quadrant pain will be randomized into two groups: twenty subjects in the control group, and twenty subjects in the intervention group. The intervention group will be further randomized into two groups: ten subjects will receive instructions for home use of TENS with daily SMS text message reminders and ten subjects will receive instructions for home use of TENS without SMS text message reminders. We will aim for an equal distribution of males and females in each group.

First session (Day 1): Before starting the procedures, participants complaining of pain that are greater than 4/10 in the VAS will be excluded from the study as this will be greater of what we consider to be subclinical pain based on literature review and if the pain has been present less than three months. In addition, if participants with pain less than 4/10 pain receiving clinical pain treatment, have taken pain medication

within six hours of first session, have acute pain or contraindications for electrical stimulation would be excluded from the study. Following completion of the signing procedures, all participants will be given brief explanations before administration of the questionnaires.

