9. DATA COLLECTION

The study will be conducted in the Neuroscience Research Laboratory in the SAHP-[name]. Informed consent will be obtained prior to

the beginning of the study by the graduate student investigator and other IRB approved researchers. Participants will be recruited if they are adults (males and females) aged 20-40 years old with no pain for the normal group and with neck or upper quadrant pain no greater than 4/10 in the VAS for longer than three months, not receiving clinical pain treatment, have not taken pain medication within six hours of first session, have acute pain or contraindications for TENS.

Study participants will be assessed on visits one, two and three (visit three will be at the end of the thirty-day period).

During participant's visit one, two and three the following clinical assessments will be provided:

- The VAS for pain, a subjective measure of pain intensity
- The STAI-form Y is a definitive clinical measure of state and trait anxiety in adults.
- The NDI questionnaire that measures neck disability.
- JPE test which will measure cervical spine proprioception through the Noraxon myoMotionTM system instrument.

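### The protocol describes no allocation concealment, and Section 8c shows participants as already assigned when they complete the VAS that decides entry

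*Protocol*

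**What the plan says.** **Sequence.** Protocol Section 7 has the forty participants with pain "randomized (random number table will be used) into two groups: twenty subjects in the control group", with the same fixed number in the intervention group. Section 8c adds: "The intervention group will be further randomized into two groups", ten with SMS reminders and ten without, and names no method for this second step. It also says: "We will aim for an equal distribution of males and females in each group". No stratification or other mechanism is attached to that aim.

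**Staff and setting.** Consent takes place "in the SAHP Neuroscience Research Laboratory with a single potential subject at a time" (Section 7) and is obtained "by the graduate student investigator and other IRB approved researchers" (Section 9). Neither document says who generates or holds the sequence, how it is concealed, or when an assignment is disclosed.

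**Eligibility.** Section 5 determines exclusions from a self-report questionnaire. The opening of the Day 1 text in Section 8c excludes on VAS before procedures begin. The following paragraphs describe people already randomised to control, to TENS with SMS and to TENS without SMS, and have each complete a VAS on which a score below 4/10 is required.

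**After assignment.** In Section 8c the control group receives no device, sham or instruction. The TENS instruction is described separately for the two SMS subgroups.

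**The concern.** Randomisation protects the comparison only if nobody can act on an assignment before the participant is irrevocably in the trial. Here enrolment is one person at a time, entry rests on self-report, and past assignments are visible because one arm gets a device and the other gets nothing. If the arm is known when the VAS is scored, three things can happen:

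- staff can accept, defer or decline someone with the arm in mind;
- a participant can be removed after assignment for failing the VAS limit, so the analysed groups are no longer the randomised groups;
- the participant can give the baseline VAS, STAI and NDI knowing whether TENS is coming, so the starting point for every change score may already differ by arm.

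Separately, if SMS status is set before the TENS instruction, the teaching may differ between the subgroups whose compliance Objective 3 compares.

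**Working it through.** **1. The plan's own figures.** The totals are consistent: 20 + 20 = 40 and 10 + 10 = 20. The plan gives no figure for predictability, so there is none to reproduce. The SAP's sample size does not bear on this point.

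**2. Order of events, side by side.**

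- Section 8c, opening of Day 1: VAS exclusion comes before procedures; its position relative to randomisation is not given.
- Section 8c, next paragraphs: assignment, including SMS status, is already made; the qualifying VAS follows, then STAI, NDI and joint position error.
- Section 8c, instruction paragraphs: TENS teaching is given to groups already defined by SMS status.
- The VAS limit itself varies. Above 4 is excluded (8c, opening), below 4 is required (8c, group paragraphs), and no greater than 4 is accepted (Section 9). A score of exactly 4 can go either way.

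On the second and third descriptions, both assignments precede the eligibility measure. The first description does not settle the matter.

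**3. What fixed totals alone reveal.** Assume past assignments are visible and the list is hidden. Let n be the number per arm and p = C(2n,n)/2^(2n), which is 0.1254 for n = 20 and 0.1762 for n = 10. The protocol does not say how the totals are reached, so two readings are shown.

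*Random permutation of n + n:*

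- Certain assignments on average = 2n/(n+1). This gives 40/21 = 1.9 of 40, and 20/11 = 1.8 of 20 for the SMS split.
- Correct best guesses = n − 0.5 + 0.5/p = 20 − 0.5 + 0.5/0.1254 = 23.5 of 40, or 59% (chance is 50%).

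*Independent draws until one arm is full:*

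- Certain assignments on average = 2n × p. This gives 40 × 0.1254 = 5.0 of 40 (simulated 95th percentile 11), and 20 × 0.1762 = 3.5 of 20 for the SMS split.
- Correct guesses = (40 − 5.0)/2 + 5.0 = 22.5 of 40, or 56%.

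If the list is open to recruiting staff, all 40 can be known.

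**4. Would small permuted blocks help?** For a block of 2m, correct guesses = m − 0.5 + 2^(2m−1)/C(2m,m). For assumed block sizes:

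- size 4: 2 − 0.5 + 8/6 = 2.83, or 71%;
- size 6: 3 − 0.5 + 32/20 = 4.10, or 68%;
- size 8: 4 − 0.5 + 128/70 = 5.33, or 67%.

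All exceed the 59% for one permutation of 20 + 20. Varying the block size helps little, because guessing the under-represented arm needs no knowledge of where blocks end.

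**5. The baseline differences in the SAP.** Two variables, STAI_T and left lateral flexion, differed significantly. The number of baseline tests is not given. Assuming k independent tests at 0.05, P(two or more) = 1 − 0.95^k − k × 0.05 × 0.95^(k−1). For k = 10 this is 1 − 0.599 − 0.315 = 0.086; for k = 15 it is 1 − 0.463 − 0.366 = 0.171.

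**The case against.** The strongest reply is that silence is not evidence of an open list. A random number table is a valid generator and does not itself disclose the next assignment. Names and some administrative pages are withheld from the public text, so whether those who consent, screen, teach and hold the sequence are the same people cannot be read from it. This stands. A reader might infer that the recruiting staff could see the next assignment, but the documents neither say so nor exclude it.

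A reader might also argue that simple draws give exactly 20:20 only 12.5% of the time, so a pre-drawn list must exist and must be readable. The first half suggests some restriction on the draws. The second does not follow, since most concealed schemes also start from a pre-drawn list.

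The SAP's two baseline differences might be taken as a sign of selection. Step 5 shows they are compatible with chance. The SAP adjusts for them by ANCOVA, which answers the measured imbalance but not imbalance in unmeasured factors.

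Finally, Section 8c may simply be narrating by group label, without meaning to time either randomisation, and its instruction text is nearly the same for both SMS subgroups. That is a fair reading, and different teaching by subgroup is a possibility only. But the same section offers a different order and the protocol never resolves it, so anyone following it as written may assign first and check eligibility second.

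**Conclusion.** The point stands as a gap in the plan with a specific defect in sequence. No concealment is described, the holder of the sequence is not stated, and the order of assignment and qualifying VAS must be reconciled within Section 8c. This is more than missing detail, because the group paragraphs, followed literally, allow exclusion after assignment and baseline self-reports with the arm known. They also have the TENS instruction given with SMS status already set, which could bias Objective 3.

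The exposure from fixed totals alone is small. Only the unstated handling of the list could make it large. The documents do not support a claim that selection occurred, and they give no basis for putting a size on any resulting bias. The conclusion assumes that the written procedure is the one followed and that past assignments were visible to staff, as the device-or-nothing design implies.

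**What to change.** 1. Have someone outside enrolment, for example the statistician foreseen in Protocol Section 11, prepare one random permutation of 20 + 20, or another restricted scheme without small blocks, in sequentially numbered, opaque, sealed envelopes.
2. Open each envelope only after consent, confirmed eligibility and all Day 1 baseline measures. Rewrite the Day 1 text of Section 8c to give this single order, and reconcile the VAS limits across Sections 8c and 9.
3. Use a second envelope for SMS or no SMS, opened only after the TENS instruction and the Day 1 lab treatment. Section 5 already excludes anyone unwilling to receive the daily text, so every randomised participant can take either subgroup.
4. State how sex balance is to be achieved, or drop the aim.

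The cost is some preparation time and a short amendment, with no extra staff or participants.

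The SAP is written in the past tense and reports baseline results, so enrolment may be over. In that case, report who held the sequence, when assignments were revealed relative to eligibility and baseline measures, and how the 10:10 split was made. State any lack of concealment as a limitation.

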8. STUDY DESIGN

a. Background or rationale for this study.

As defined by the International Association for the Study of Pain (IASP) pain is “an unpleasant sensory and emotional experience associated with, or resembling that associated with, actual or potential tissue damage.” (IASP, 2021) and one of the most

common reasons people seek medical care is chronic pain. Approximately 50 million adults in United States have chronic pain affecting daily lives¹ posing public health problems in costs of pharmacological management.^{2,3} The financial cost to care for people with chronic pain is more costly than diabetes, cardiovascular and cancer combined.^{4,5}

Chronic pain is persistent or recurrent pain that last longer than 3 months in one or more locations in the body even beyond the period of the expected healing phase.^{6,7} Chronic pain can be affected by biological, psychological, and social factors that are accompanied by anxiety, depression, frustration, deconditioning, functional disability, financial problems and opioid use problems.^{8,9} As people experience pain, that experience and manifestation of pain is unique to each individual and includes physical and psychological factors⁷ making the managing pain and chronic pain can a difficult thing to achieve.¹

Facing an opioid epidemic, the Centers of Disease Control and Prevention (CDC) reports that studies of 2 weeks to 6 months in duration that utilized effective non-pharmacological treatments for chronic pain were effective.¹⁰ Among the recommendations from the CDC for non-opioid and non-pharmacological treatments for pain, physical therapy is included.^{10,11} As physical therapists we find imperative to reinforce the use of non-pharmacologic options for pain relief in people that are tackling the difficult task of managing their pain to continue with their normal lives.

As mentioned previously, one of the most common reasons people seek medical care is chronic pain;¹ however, subclinical pain (mild, low irritability) generally does not prompt people to seek medical treatment.^{12,13,14} Subclinical pain can be measured by the visual analog scale (VAS) score of $\leq 3.4/10$.¹⁵ In addition, non-pharmacological treatments in physical therapy for chronic subclinical pain have not been studied extensively. Pain can lead to anxiety (which is often treated with pharmacological interventions) and avoidance of movement.^{8,9} Pain and local inflammation in the cervical spine or upper quadrant, coupled with avoidance of movement, can lead to reduced cervical spine proprioception. Pain and anxiety are often treated with pharmacological interventions.

We are interested in learning more about people living with “subclinical” pain. According to Grant et al and Browne et al.^{16,17} people with neck pain but are not yet receiving any treatment as having minor musculoskeletal or “subclinical” pain.

Subclinical pain may increase anxiety^{18,19} and affect movement and can lead to anxiety, disability, and impaired neck proprioception.^{12,14,20,21}

People may ask what those non-pharmacologic options that physical therapy can offer for pain management, especially for untreated subclinical pain? In the field of physical therapy biophysical agents are agents that apply forms of energy to “modulate or decrease pain” along with the reduction of “risk factors and complications; enhance health, wellness, or fitness; enhance or maintain physical performance; or prevent or remediate impairments in body functions and structures, activity limitations, or participation restrictions.”²² Within the group of biophysical agents is the application and use of electrical currents, more specifically transcutaneous electrical nerve stimulation (TENS).²²

TENS is the delivery of electrical current through intact skin to stimulate peripheral nerves.²³ TENS delivers electrical currents through the skin with the objective to stimulate peripheral nerves to prevent the transmission of nociceptive information to the brain and by this process achieve pain relief.^{24,25,26,27} One of the most accepted theories for the modulation of pain with the use of TENS is the “gate control theory of pain” by Melzack and Wall published in 1965.^{28,29} which explains pain relief by electrical stimulation.²⁸ The authors proposed that by using electrical currents to stimulate low-threshold A-beta axons, it will reduce pain by preventing the transmission of nociceptive information in the spinal cord and brainstem.²³ This theory also proposed that the substantia gelatinosa (SG) in the dorsal horn of the spine acts as a gate control system before afferents influence T cells.²⁸ T cells then activate the system responsible for response and perception.²⁸ Large-diameter afferent nerve fibers (facilitates SG) and small-diameter afferent nerve fibers (inhibits SG) influence T cells.³⁰ TENS gives the clinician the option to select the depolarization of afferents nerves through the adjustment of parameters of electrical current delivered with electrodes through the skin.³⁰ Depolarizing large-diameter (A-beta) sensory afferent nerves via sensory TENS can help gate or block noxious input.^{30,31,32} TENS has been used for treating subclinical pain based on studies that have found superiority of TENS over placebo for chronic musculoskeletal pain.³³ Most importantly for our study, TENS is a non-prescriptive battery-powered device that uses self-adhering electrodes on the surface of the skin to deliver electrical current. TENS is often self-administered, affordable and safe when compared to medications.²³

Despite electrical stimulation for pain modulation has been used for many years, there is an “efficacy-impasse” for clinical utilization of TENS, despite fifty years of published research.³⁴ There is an urgent need for randomized controlled trials to investigate TENS effectiveness.³⁴ Based on this need the purpose of this study is to investigate the effects of electrotherapy for improving cervical spine proprioception, reduce pain, anxiety, and disability in adults with subclinical neck or upper quadrant pain.

b. Objectives.

- 1) To measure the immediate and short-term effects of TENS on subclinical neck or upper quadrant pain with the VAS, anxiety with the State-Trait Anxiety Inventory for Adults™, disability with neck disability index (NDI), disability and cervical spine proprioception Noraxon 3D Inertial Motion Capture System in subjects 20-40 years of age.
- 2) To measure pain, anxiety, disability, and cervical spine proprioception in subjects with and without neck or upper quadrant pain.
- 3) To compare compliance of TENS home usage in groups with and without short message system (SMS), text message, reminders.

c. Procedures involved (Research Interventions)

There will be three groups as follows: twenty subjects with no pain in the normal group; forty subjects with chronic subclinical neck or upper quadrant pain will be randomized into two groups: twenty subjects in the control group, and twenty subjects in the intervention group. The intervention group will be further randomized into two groups: ten subjects will receive instructions for home use of TENS with daily SMS text message reminders and ten subjects will receive instructions for home use of TENS without SMS text message reminders. We will aim for an equal distribution of males and females in each group.

First session (Day 1): Before starting the procedures, participants complaining of pain that are greater than 4/10 in the VAS will be excluded from the study as this will be greater of what we consider to be subclinical pain based on literature review and if the pain has been present less than three months. In addition, if participants with pain less than 4/10 pain receiving clinical pain treatment, have taken pain medication

within six hours of first session, have acute pain or contraindications for electrical stimulation would be excluded from the study. Following completion of the signing procedures, all participants will be given brief explanations before administration of the questionnaires.

First, participants in the normal group (20 subjects) will first be instructed to complete the VAS for pain, a subjective measure of pain intensity consisting of a 10 centimeter (cm) line with anchor statements on the left (no pain) and extreme pain on the right. Pain scores will be determined by measuring the distance in cm from “no pain” to the participant’s anchor point. In this group the score must be “no pain” or 0 cm. Participants randomly assigned to the control group (20 subjects) will first be instructed to complete the VAS for pain with a score less than 4/10 required. Participants randomly assigned to the intervention group (10 subjects) that will receive daily SMS text message reminders for compliance during intervention will first be instructed to complete the VAS for pain with a score less than 4/10 required. Participants randomly assigned to the intervention group (10 subjects) that will not receive daily SMS text message reminders for compliance during intervention will first be instructed to complete the VAS for pain with a score less than 4/10 required.

Next, all participants in all groups will complete 2 self-report questionnaires beginning with the STAI-form Y which is a definitive clinical measure of state and trait anxiety in adults. Form Y has 20 items for assessing trait anxiety and 20 for state anxiety. All items are rated on a 4-point scale (e.g., from “Almost Never” to “Almost Always”). Higher scores indicate greater anxiety.

Next, all participants in all groups will complete the NDI questionnaire which consist of 10 sections (pain intensity, personal care, lifting, work, headaches, concentration, sleeping, driving, reading and recreation) with questions that are measure in a 6-point scale from 0 (no disability) to 5 (full disability). The numeric responses will be added with a score varying from 0-50 where 0 is considered “no activity limitation” and 50 is considered “complete disability.” Furthermore, 0-4 (no disability), 5-14 (mild disability), 15-24 (moderate disability), 25-34 (severe disability) and greater than 35 (complete disability).

Next, all participants in all groups will be familiarized with the Noraxon myoMotion™ system instrument that utilizes inertial measurement units (IMUs) to

measure angles of motion in joints which will measure cervical spine proprioception utilizing the joint position error (JPE) test.

Participants in the normal group will not receive any interventions in the lab or at home and will not receive education on the use of TENS equipment.

Participants in the control group will not receive any interventions in the lab or at home and will not receive education on the use of TENS equipment.

Participants in the intervention group with daily SMS text message reminders will be provided with a TENS unit by the investigators for home use for a total of 29 days and instructed by a licensed physical therapist for its use and safety. In addition, you will be provided with a daily log sheet to track its use while receiving SMS text message reminders for compliance. Then, the participants in this intervention group will receive a 30-minute high-frequency sensory TENS treatment in lab on the pain site in the neck and upper quadrant area. After the 30-minute high-frequency sensory TENS treatment, the participants in the intervention group will again complete the VAS, STAI, and NDI. Also, cervical spine proprioception will be measured with Noraxon myoMotionTM system instrument utilizing the JPE test.

Participants in the intervention group without daily SMS text message reminders will be provided with a TENS unit by the investigators for home use for a total of 29 days and instructed by a licensed physical therapist for its use and safety. In addition, you will be provided with a daily log sheet to track its use without receiving SMS text message reminders for compliance. Then, the participants in this intervention group will receive a 30-minute high-frequency sensory TENS treatment in lab on the pain site in the neck and upper quadrant area. After the 30-minute high-frequency sensory TENS treatment, the participants in the intervention group will again complete the VAS, STAI, and NDI. Also, cervical spine proprioception will be measured with Noraxon myoMotionTM system instrument utilizing the JPE test.

Session 2 (1st follow up) (Day 8): Participants will return on day eight. Participants in the normal group will be asked to complete again complete the VAS, STAI, and NDI. Also, cervical spine proprioception will be measured with Noraxon myoMotionTM system instrument utilizing the JPE test. Participants will not receive any interventions in the lab.

Participants in the control group will be asked to complete again complete the VAS, STAI, and NDI. Also, cervical spine proprioception will be measured with

Noraxon myoMotionTM system instrument utilizing the JPE test. Participants will not receive any interventions in the lab.

Participants in the intervention group with daily SMS text message reminders will be asked to complete again complete the VAS, STAI, and NDI. Also, cervical spine proprioception will be measured with Noraxon myoMotionTM system instrument utilizing the JPE test. Participants will not receive any interventions in the lab.

Participants in the intervention group without daily SMS text message reminders will be asked to complete again complete the VAS, STAI, and NDI. Also, cervical spine proprioception will be measured with Noraxon myoMotionTM system instrument utilizing the JPE test. Participants will not receive any interventions in the lab.

Phone/Email follow up: Participants in the normal, control and intervention (with no SMS text message reminders) groups will be contacted by e-mail and SMS text message during the seventh day period at least one before returning for session two on the eight day and at least three times before returning for the last session on day thirty.

Participants in the intervention group (with SMS text reminders for compliance) will be contacted via SMS text message daily for compliance with high-frequency sensory TENS during the seven-day period before session two and during the twenty-one-day period before last session. We will send a text message to the personal phone. Investigators will be available through phone, text message or email to answer any questions participants may have.

Last session (Day 30): Participants will return on day thirty. Participants in the normal group will be asked to complete again complete the VAS, STAI, and NDI. Also, cervical spine proprioception will be measured with Noraxon myoMotionTM system instrument utilizing the JPE test. Participants will not receive any interventions in the lab and will be given a \$50 gift card.

Participants in the control group will be asked to complete again complete the VAS, STAI, and NDI. Also, cervical spine proprioception will be measured with Noraxon myoMotionTM system instrument utilizing the JPE test. Participants will not receive any interventions in the lab and will be given a \$50 gift card.

Participants in the intervention group with daily SMS text message reminders will be asked to complete again complete the VAS, STAI, and NDI. Also, cervical spine proprioception will be measured with Noraxon myoMotionTM system instrument utilizing the JPE test. They will return the TENS unit and the daily log sheet to the investigators. Participants will not receive any interventions in the lab. and will be given a \$50 gift card.

Participants in the intervention group without daily SMS text message reminders will be asked to complete again complete the VAS, STAI, and NDI. Also, cervical spine proprioception will be measured with Noraxon myoMotionTM system instrument utilizing the JPE test. They will return the TENS unit and the daily log sheet to the investigators. Participants will not receive any interventions in the lab. and will be given a \$50 gift card.

- d. Alternative procedures, if any, that are not included in the study but might be advantageous to the subject.

n/a

- e. Concise review of literature that supports the rationale, objectives, and methodology of the proposed study.

As defined by the IASP pain is “an unpleasant sensory and emotional experience associated with, or resembling that associated with, actual or potential tissue damage.” (IASP, 2021) and one of the most common reasons people seek medical care is chronic pain. Approximately 50 million adults in United Stated have chronic pain affecting daily lives¹ posing public health problems in costs of pharmacological management.^{2,3} The financial cost to care for people with chronic pain is more costly than diabetes, cardiovascular and cancer combined.^{4,5}

Chronic pain is persistent or recurrent pain that last longer than 3 months in one or more locations in the body even beyond the period of the expected healing phase.^{6,7} Chronic pain can be affected by biological, psychological and social factors that are accompanied by anxiety, depression, frustration, deconditioning, functional disability, financial problems and opioid use problems.^{8,9} As people experience pain, that experience and manifestation of pain is unique to each individual and includes physical and psychological factors⁷ making the managing pain and chronic pain can a difficult thing to achieve.¹

Facing an opioid epidemic, the CDC reports that studies of 2 weeks to 6 months in duration that utilized effective non-pharmacological treatments for chronic pain were effective.¹⁰ Among the recommendations from the CDC for non-opioid and non-pharmacological treatments for pain, physical therapy is included.^{10,11} As physical therapists we find imperative to reinforce the use of non-pharmacologic options for pain relief in people that are tackling the difficult task of managing their pain to continue with their normal lives.

As mentioned previously, one of the most common reasons people seek medical care is chronic pain;¹ however, subclinical pain (mild, low irritability) generally does not prompt people to seek medical treatment^{12,13,14} Subclinical pain can be measured by the VAS score of $\leq 3.4/10$.¹⁵ In addition, non-pharmacological treatments in physical therapy for chronic subclinical pain have not been studied extensively. Pain can lead to anxiety^{8,9} (which is often treated with pharmacological interventions) and avoidance of movement. Pain and local inflammation in the cervical spine or upper quadrant, coupled with avoidance of movement, can lead to reduced cervical spine proprioception. Pain and anxiety are often treated with pharmacological interventions.

We are interested in learning more about people living with “subclinical” pain. According to Grant et al and Browne et al.^{16,17} people with neck pain but are not yet receiving any treatment as having minor musculoskeletal or “subclinical” pain. Subclinical pain may increase anxiety^{18,19} and affect movement and also can lead to anxiety, disability and impaired neck proprioception^{12,14,20,21}

People may ask what those non-pharmacologic options that physical therapy can offer for pain management, especially for untreated subclinical pain? In the field of physical therapy biophysical agents are agents that apply forms of energy to “modulate or decrease pain” along with the reduction of “risk factors and complications; enhance health, wellness, or fitness; enhance or maintain physical performance; or prevent or remediate impairments in body functions and structures, activity limitations, or participation restrictions.”²² Within the group of biophysical agents is the application and use of electrical currents, more specifically TENS.²²

TENS is the delivery of electrical current through intact skin to stimulate peripheral nerves.²³ TENS delivers electrical currents through the skin with the objective to stimulate peripheral nerves to prevent the transmission of nociceptive information to the brain and by this process achieve pain relief.^{24,25,26,27} One of the

most accepted theories for the modulation of pain with the use of TENS is the “gate control theory of pain” by Melzack and Wall published in 1965.^{28,29} which explains pain relief by electrical stimulation.²⁸ The authors proposed that by using electrical currents to stimulate low-threshold A-beta axons, it will reduce pain by pre-venting the transmission of nociceptive information in the spinal cord and brainstem.²³ This theory also proposed that the SG in the dorsal horn of the spine acts as a gate control system before afferents influence T cells.²⁸ T cells then activate the system responsible for response and perception.²⁸ Large-diameter afferent nerve fibers (facilitates SG) and small-diameter afferent nerve fibers (inhibits SG) influence T cells.³⁰ TENS gives the clinician the option to select the depolarization of afferents nerves through the adjustment of parameters of electrical current deliver with electrodes through the skin.³⁰ Depolarizing large-diameter (A-beta) sensory afferent nerves via sensory TENS can help gate or block noxious input.^{30,31,32} TENS has been used for treating subclinical pain based on studies that have found superiority of TENS over placebo for chronic musculoskeletal pain.³³ Most importantly for our study, TENS is non-prescriptive battery-powered device that uses self-adhering electrodes on the surface of the skin to deliver electrical current. TENS is often self-administered, affordable and safe when compared to medications.²³

Despite electrical stimulation for pain modulation has been used for many years, there is an “efficacy-impasse” for clinical utilization of TENS, despite fifty years of published research.³⁴ There is an urgent need for randomized controlled trials to investigate TENS effectiveness.³⁴ Based on this need the purpose of this study is to investigate the effects of electrotherapy for improving cervical spine proprioception, reduce pain, anxiety, and disability in adults with subclinical neck or upper quadrant pain.

- f. If an Investigational Device (ID) is involved, provide the following information:
 - (1) name of device, (2) manufacturer, (3) status with Food and Drug Administration and ID#, (4) review of animal studies and previous human studies, (5) reported adverse effects.

n/a

